7.2. PROCEDURES FOR RECORDING AND REPORTING ADVERSE EVENTS

7.2.1. Adverse Event Recording

Each subject must be carefully monitored for the development of any AEs. This information should be obtained in the form of non-leading questions (eg, “How are you feeling?”) and from signs and symptoms detected during each assessment, observations of study personnel, and spontaneous reports from subjects.

After the ICF is signed, site personnel will note any change in the condition(s) and the occurrence and nature of any AEs. From the signing of the study informed consent form until the first dose of bezuclastinib, only SAEs and AEs considered related to on-protocol procedures will be collected. TEAEs will be recorded from the start of study treatment until 30 days after the last dose of study drug.

All AEs (serious and non-serious) will be monitored until resolved, stabilized, or returned to baseline status during study participation.

After receipt of any study drug, all AEs spontaneously reported by the subject and/or in response to an open question from the study personnel or revealed by observation will be recorded via eCRF.

Laboratory abnormalities or other abnormal assessments (eg, physical examination findings, vital signs, ECGs) should only be recorded as AEs if clinically significant (ie, requiring medical or surgical intervention); abnormalities that lead to investigational therapy discontinuation, delay, or interruption; or abnormalities associated with clinical signs or symptoms.

Whenever possible, the clinical diagnosis, rather than the laboratory result or signs and symptoms, should be reported by the Investigator (eg, anemia vs decreased hematocrit) as 1 comprehensive event.

If a constellation of signs and/or symptoms cannot be medically characterized as a single diagnosis or syndrome at the time of reporting, each individual event should be recorded on the eCRF. If a diagnosis is subsequently established, all previously reported AEs should be replaced based on the single diagnosis.

The AE term should be reported in standard medical terminology when possible.

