1.4. BENEFIT/RISK ASSESSMENT

AdvSM is a serious and life-threatening disease that involves the rapid and abnormal proliferation of a clonal mast cell population. Depending on the subtype of AdvSM, the average life-expectancy of a patient can range from 2 to 41 months ([NCCN Systemic Mastocytosis, Version 2.2019](#); [Rossignol et al, 2019](#)). The pathogenesis of AdvSM is driven by activation of the KIT receptor, specifically through a mutation in exon 17 (D816V). There are approved therapies targeting *KIT* mutations in some regions for the treatment of patients with AdvSM; however, significant safety and tolerability issues have limited their use.

Bezuclastinib is a TKI that selectively targets *KIT* mutations, including D816V, as reported in nonclinical studies. Preliminary clinical activity with bezuclastinib has been observed in clinical Study PLX121-01 in subjects with solid tumors including GIST. A reduction in KIT exon 17 mutational burden was observed in subjects treated with bezuclastinib in that study, and this reduction was temporally associated with a reduction in tumor burden. Based on available clinical PK and nonclinical pharmacology data, it is expected that all dose levels to be studied may generate trough concentrations greater than IC₅₀ for *KIT* D816V, and therefore have the potential to be clinically active.

Upon initiation of this clinical study, a total of 78 healthy volunteers and subjects with solid tumors have received bezuclastinib as a single agent or in combination with pexidartinib or sunitinib across 2 clinical studies. Safety data indicate that bezuclastinib has acceptable safety and tolerability at total daily doses up to 1000 mg as a single agent or in combination with sunitinib. The important potential risks associated with bezuclastinib, which include hepatotoxicity (ie, asymptomatic elevations in liver enzymes), hematological toxicity (ie, anemia, thrombocytopenia, and neutropenia) and gastrointestinal toxicity (ie, nausea, vomiting, and diarrhea), were selected based on bezuclastinib nonclinical safety data, clinical experience, and the assessment of risks for products with similar mechanisms. AEs observed with bezuclastinib in the completed clinical studies were primarily low-grade, non-serious, reversible, and manageable via recommended dose modifications.

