Anemia, neutropenia, thrombocytopenia (a)	Grade 4 anemia for ≥7 days Grade 4 neutropenia for ≥7 days, or Grade 3 or worse neutropenia associated with bacterial or fungal infection requiring systemic therapy Febrile neutropenia (any grade) Grade 4 thrombocytopenia for ≥7 days, or Grade 3 or worse thrombocytopenia associated with bleeding	Hold bezuclastinib until resolved to ≤Grade 1 or baseline. If recovered to ≤Grade 1 or baseline in ≤28 days, reduce by 1 dose level. If not recovered to ≤Grade 1 or baseline after 28 days, discontinue study drug.

Table 6: Dose Modification Criteria for TEAEs At Least Possibly Related to Bezuclastinib

TEAE	Criteria or CTCAE v5.0 Grade	Dose Modification
ECG QT prolonged	Grade 3: >500 msec or >60 msec increase from baseline (b)	Hold bezuclastinib until QTc ≤500 msec (≤Grade 2); then reduce by 1 dose level If not recovered to ≤Grade 1 or baseline after 28 days, discontinue study drug.
	Grade 4: Torsade de pointes, polymorphic ventricular tachycardia, or signs/symptoms of serious arrhythmia	Permanently discontinue study drug.
Transaminase increases	ALT or AST >8×ULN ALT or AST >5×ULN for more than 2 weeks ALT or AST >3×ULN and TBL >2×ULN or INR >1.5 ALT or AST >3×ULN with the appearance of fatigue, nausea, vomiting, right upper quadrant pain or tenderness, fever, rash, and/or eosinophilia (>5%)	Consider the possibility of drug-induced liver injury. If drug-induced liver injury is suspected, permanently discontinue study drug if it is in the best interest of the subject.
Other non-hematological toxicity (excluding Grade 3 nausea, vomiting, or diarrhea lasting ≤72 hours with adequate prophylactic and supportive care), including clinically significant non-hematologic laboratory parameters (excluding elevations in alkaline phosphatase)	Grade 3	Hold bezuclastinib until resolved to ≤Grade 1 or baseline. If recovered to ≤Grade 1 or baseline in ≤28 days, reduce by 1 dose level. If not recovered to ≤Grade 1 or baseline after 28 days, discontinue study drug.
	Grade 4	Permanently discontinue study drug unless considered unrelated to treatment.

Abbreviations: AE=adverse event, ALT=alanine transaminase, AST=aminotransferase, CTCAE=National Cancer Institute Common Terminology for Adverse Events, ECG=electrocardiogram, MCL=mast cell leukemia, QTc=corrected QT interval, TBL=total bilirubin, TEAE=treatment-emergent adverse event, ULN=upper limit of normal.

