7. SAFETY DATA COLLECTION, RECORDING, AND REPORTING

7.1. ADVERSE EVENTS

7.1.1. Definition of an Adverse Event

An AE is any untoward medical occurrence in a patient or clinical investigation subject administered a pharmaceutical product and that does not necessarily have a causal relationship with this treatment. An AE can therefore be an unfavorable and unintended sign (including an abnormal laboratory finding), symptom, or disease temporarily associated with the use of a medicinal (investigational) product, whether or not related to the medicinal (investigational) product.

An AE can arise from any use of the medicinal (investigational) product and from any route of administration, formulation, or dose, including overdose. The definition of an AE also covers medication errors and uses outside what is foreseen in the protocol, including misuse and abuse of the product.

Situations where an untoward medical occurrence did not occur (social and/or convenience admission to a hospital) and anticipated day-to-day fluctuations of pre-existing disease(s) or condition(s) present or detected at the start of the study that do not worsen are not AEs.

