7.1.3. Adverse Events of Clinical Interest

AEs of clinical interest in this study are defined as the following AEs of Grade 3 or higher severity regardless of causality or seriousness: QTc prolongation, hepatic events, and bleeding events.

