8.9. SAFETY ANALYSES

Safety will be assessed by vital signs, hematology and chemistry laboratory evaluations, ECGs, and AEs, including all TEAEs, treatment-related AEs, SAEs, and AEs leading to dose modification.

The primary safety endpoint is the incidence of TEAEs. The secondary safety endpoints include extent of exposure (PK), changes in laboratory parameters, and changes in ECGs.

AEs will be reported according to the NCI CTCAE version 5.0 or higher and coded according to the latest MedDRA version available at the time of database creation. The number and percent of subjects with any AE will be presented by System Organ Class and Preferred Term for each cohort and will be summarized by cohort. Vital signs, laboratory parameters, and ECG intervals will be summarized and listed by timepoint by study part.

AEs will be categorized according to MedDRA System Organ Class and Preferred Term. Additional subcategories will be based on event intensity (severity graded according to NCI CTCAE version 5.0) and relationship to study drug.

Deaths, SAEs, AEs of clinical interest, and AEs leading to study drug discontinuation will be tabulated on a per subject basis, as warranted by the data. These endpoints will be listed.

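### Section 7.2.1 lets an asymptomatic, untreated Grade ≥3 transaminase rise with dosing continued escape both TEAE incidence and the expedited reporting that 7.1.3 sets for hepatic events

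*Protocol*

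**What the plan says.** Section 7.2.1 limits which laboratory, ECG and other assessment abnormalities become AEs. They "should only be recorded as AEs if clinically significant (ie, requiring medical or surgical intervention". The alternatives are "abnormalities that lead to investigational therapy discontinuation, delay, or interruption; or abnormalities associated with clinical signs or symptoms". CTCAE grade is not among the criteria, and neither is dose reduction.

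Other sections bear on the same events:

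- Section 7.1.1 takes a wider view: "An AE can therefore be an unfavorable and unintended sign (including an abnormal laboratory finding), symptom, or disease".
- Section 1.4 lists the important potential risks as "hepatotoxicity (ie, asymptomatic elevations in liver enzymes), hematological toxicity (ie, anemia, thrombocytopenia, and neutropenia", together with gastrointestinal toxicity.
- Section 7.1.3 defines events of clinical interest as "AEs of Grade 3 or higher severity regardless of causality or seriousness: QTc prolongation, hepatic events, and bleeding events". Section 7.2.5 puts these on the SAE timelines, which Section 7.2.4 sets at 24 hours.
- Section 8.9 states: "The primary safety endpoint is the incidence of TEAEs". It continues: "The secondary safety endpoints include extent of exposure (PK), changes in laboratory parameters, and changes in ECGs".
- Section 2 makes AE incidence, laboratory changes and dose modifications part of the primary endpoints of Part 1 and Part 2 Stage 1. AEs leading to dose modifications are a secondary endpoint throughout.

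**The concern.** The hepatic risk in Section 1.4 is described as asymptomatic, and absence of symptoms is one of the features that keeps an abnormality out of the AE record under 7.2.1. A raised ALT or AST then becomes an AE only if somebody treats it or stops or pauses the drug. Section 7.1.3 sets causality and seriousness aside so that the sponsor hears promptly of every severe hepatic or QTc event, but it is written in terms of AEs. What 7.2.1 keeps out of the AE record never reaches 7.1.3.

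Two things are at stake: the completeness of hepatic event counts in the primary safety endpoint, and timely notice of severe hepatic values. Whether a given value counts also depends partly on how readily each site intervenes, so the same result may be an AE at one site and not at another. The signal is plausible: Section 1.2.2 reports AST increase among the commonest TEAEs in the earlier single-agent solid-tumour study.

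**Working it through.** The protocol gives no figure to reproduce. The check follows four kinds of abnormality through the recording rule (7.2.1), Table 6 in Section 5.6, the clinical-interest list (7.1.3) and the endpoints (8.9).

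**1. Grade ≥3 ALT/AST rise, no symptoms, no treatment, dosing continued.**
- 7.2.1: no route is met, so it is not an AE.
- Table 6: the transaminase row asks the investigator to do this: "Consider the possibility of drug-induced liver injury". Discontinuation follows only if such injury is suspected and stopping is in the subject's interest. The row requires no hold at any multiple of ULN, so the result does not depend on where Grade 3 begins, a cut-off the protocol does not give.
- Table 6 is also confined to TEAEs at least possibly related to drug. It takes AE status as given, while 7.2.1 would confer that status through an interruption of dosing.
- Result: absent from TEAE incidence and from 24-hour reporting.

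**2. Grade 3 QTc prolongation, no symptoms.**
- At least possibly related: Table 6 calls for a hold. If the drug is held, the event is an AE and of clinical interest.
- Judged unrelated: Table 6 does not apply. If nobody acts, no 7.2.1 route is met, although 7.1.3 disregards causality.
- Result: a gap in principle, limited to unrelated events that are not acted on.

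**3. Cytopenia without complications, untreated, dosing continued.**
- Table 6 calls for a hold at Grade 4 lasting at least 7 days, at Grade 3 or worse with specified infection (neutropenia) or bleeding (thrombocytopenia), and for febrile neutropenia. Footnote (a) relaxes this for mast cell leukemia and for Grade 3 cytopenia at Screening.
- Outside those triggers, and if nothing else is done, it is not an AE.
- 7.1.3 does not list cytopenias.
- Result: absent from TEAE incidence; nothing changes for clinical-interest reporting.

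**4. Abnormality that leads only to a dose reduction.**
- Reduction is not a qualifying consequence in 7.2.1. In the cytopenia, QT and other Grade 3 rows of Table 6 a hold comes before the reduction, so those events already qualify through interruption.
- Result: a small gap, for reductions made without a hold.

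**Sensitivity of a rate to one uncounted subject.** The change is 1/n in the rate of that event type. With about 28/4 = 7 per Part 1 cohort it is 1/7 = 14.3 percentage points; with about 10 per Stage 1 arm, 1/10 = 10 points; with 55 to 70 in Stage 2 (55 evaluable plus up to 15 non-evaluable), 1/55 = 1.8 to 1/70 = 1.4 points. Overall TEAE incidence does not move if that subject has any other TEAE. The number of such subjects cannot be derived from the protocol.

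**The case against.** A clinical-significance filter on laboratory AEs is a legitimate design choice, and much can be said for this one.

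- **The data are not lost.** Laboratory changes are primary endpoints in Part 1 and Stage 1, and laboratory and ECG changes are secondary safety endpoints. The notes to Table 1 say that unscheduled assessments go into the eCRF. Worst-grade tables may well be in the SAP. This stands, and it rules out the inference that these toxicities vanish from the safety evaluation or that dose selection rests on AE counts alone. It does not supply 24-hour notice, and no analysis can restore an AE that sites were told not to record.
- **No required hold does not mean no AE.** Section 7.2.1 asks what actually happened. Table 6 is a recommendation, and a site may pause dosing, transfuse, or give the G-CSF that Section 5.7.2 permits; each would make the event an AE. This stands. The gap covers only events on which nobody acts.
- **Another row of Table 6 may catch the enzyme rise.** The row for other non-hematological toxicity covers clinically significant laboratory parameters, exempts only alkaline phosphatase by name, and calls for a hold at Grade 3. That is arguable. But transaminases have their own row, and 7.2.1 explains clinical significance as a need for intervention, so the gap is not clearly closed.
- **Recording every Grade ≥3 value would count the disease.** Cytopenias and liver abnormalities are baseline disease findings here (Appendix C), and Section 7.2.6.2 makes a pre-existing condition an AE only if it worsens. This stands, and it shapes the remedy.

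A reader might also infer that cytopenias lose expedited reporting. They do not: they were never on the clinical-interest list.

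**Conclusion.** The concern holds in a limited form. Section 7.2.1 conflicts with 7.1.1, with 7.1.3 and 7.2.5, and with the risk named in 1.4. The clearest consequence is hepatic: a Grade ≥3 transaminase rise that is asymptomatic, untreated and dosed through can miss both the primary safety endpoint and the expedited route. For QTc the gap exists only where the event is judged unrelated and not acted on. For uncomplicated cytopenias it concerns TEAE incidence alone.

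This rests on reading 7.2.1 literally and on 7.1.3 applying only to recorded AEs. The loss is in AE counts and prompt notice, not in the laboratory or ECG data. Its direction is toward lower AE rates; its size cannot be estimated from the protocol. It should be corrected, but it does not undermine the safety evaluation as a whole.

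**What to change.** Change recording and reporting only:

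1. In 7.2.1 and 7.1.3, state that a treatment-emergent Grade ≥3 hepatic laboratory or QTc abnormality that has worsened from baseline is recorded as an AE and qualifies as an event of clinical interest, regardless of intervention, symptoms or effect on dosing.
2. In 7.2.1, add dose reduction to the qualifying consequences, because AEs leading to dose modification are an endpoint.
3. Word the worsening condition consistently with 7.2.6.2, so that unchanged disease findings are not counted.
4. Reconcile the wording of 7.1.1, 7.1.3, 7.2.1 and Table 6 without altering any dosing rule.

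The cost is a few sentences of protocol text and matching eCRF guidance. The downside is more AE entries, more expedited reports and somewhat less favourable AE rates.

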7.2.2. Severity Assessment

AE severity will be graded using the NCI-CTCAE v5.0.

If the intensity (grade) changes within a day, the maximum intensity (grade) should be recorded. If the intensity (grade) changes over a longer period of time, the changes should be recorded as separate events (with separate onset and stop dates for each grade).

Severity and seriousness must be differentiated: severity describes the intensity of an AE, while the term seriousness refers to an AE that has met the criteria for an SAE.

7.2.3. Causality Assessment

Investigators should use their knowledge of the subject, the circumstances surrounding the event, and an evaluation of any potential alternative causes to determine whether or not an AE is considered to be related to the study treatment.

Investigators will be instructed to report their assessment of the potential relatedness of each AE to bezuclastinib via eCRF.

An Investigator causality assessment (Not Related, Unlikely Related, Possibly Related, or Related) must be provided for all AEs (both serious and non-serious). This assessment must be recorded in the eCRF and SAE forms as appropriate.

Not Related/Unrelated	Exposure to the study treatment did not occur, or the occurrence of the AE is not reasonably related in time, or the AE is considered unlikely to be related to the study treatment
Unlikely Related	The study treatment and the AE were not closely related in time, and/or the AE could be explained more consistently by causes other than exposure to the study treatment product
Possibly Related	The study treatment and the AE were reasonably related in time, and the AE could be explained equally well by causes other than exposure to the study treatment product
Related	The study treatment and the AE were reasonably related in time, and the AE was more likely explained by exposure to the study product than by other causes, or the study treatment was the most likely cause of the AE

7.2.4. Serious Adverse Event Reporting

All SAEs that occur following the signing of informed consent are to be reported within 24 hours from the point in time when the Investigator becomes aware of the SAE. This 24-hour notification requirement refers to the initial SAE information and all follow-up SAE information. All SAEs must be reported whether or not they are considered causally related to the investigational product. SAE forms will be provided to each clinical site. The information collected will include subject number, a narrative description of the event and an assessment by

the Investigator as to the severity of the event and relatedness to bezuclastinib. Follow-up information on the SAE may be requested by the Sponsor or its designee.

Any SAE that is ongoing when the subject completes or discontinues the study (with the exception of subjects who withdraw consent) will be followed by the Investigator until the event has resolved, stabilized, or returned to baseline status.

Contact information for reporting SAEs is provided in the Operations Manual.

If an Investigator becomes aware of an SAE after the subject's participation in the study has ended that is considered related to study treatment, the Investigator should report the SAEs to the Sponsor.

7.2.5. Adverse Events of Clinical Interest Reporting

AEs of clinical interest are to be reported to the Sponsor per the same timelines and methods as SAEs.

7.2.6. Suspected Unexpected Serious Adverse Reactions

Suspected unexpected serious adverse reactions (SUSARs) are SAEs that are considered at least possibly related to the investigational product or procedure by the Investigator and are not consistent in nature or severity with the reference safety information contained within the IB. Expectedness for bezuclastinib will be assessed per the reference safety information contained in the current bezuclastinib IB.

The United States 21 Code of Federal Regulations 312.32 and European Union Clinical Trials Regulation and the associated detailed guidance or national regulatory requirements in participating countries require the reporting of SUSARs; the Sponsor has procedures that will be followed for the recording and expedited reporting of SUSARs that are consistent with global regulations and the associated detailed guidances.

7.2.6.1. Deaths

All on-treatment deaths, regardless of relationship to study treatment, will be reported within 24 hours per SAE reporting guidelines, with the exception of deaths due to disease progression (as noted above).

Death should be considered an outcome and not a distinct event. The underlying medical diagnosis or suspected diagnosis that caused or contributed to the fatal outcome should be reported when possible.

7.2.6.2. Pre-existing Medical Conditions

A pre-existing medical condition is one that is present during screening or before the first administration of study drug. Such conditions should be recorded on the Medical History eCRF. A pre-existing medical condition should be recorded as an AE only if the frequency, severity, or character of the condition worsens after study treatment has been administered.

7.2.6.3. Overdose or Incorrect Administration

Any study treatment overdose or incorrect administration should be noted on the eCRF.

An overdose or incorrect administration is not an AE unless it results in untoward medical effects.

7.2.6.4. Exposure During Pregnancy

Pregnancy data will be collected during this study for all subjects. Exposure during pregnancy (also referred to as exposure in utero) can be the result of either maternal exposure or transmission of drug product via semen following paternal exposure. All pregnancies occurring following exposure to bezuclastinib (in subjects or female partners of subjects) are to be reported in the same time frame as SAEs using the Pregnancy Report Form. The course of all pregnancies, including perinatal and neonatal outcome, regardless of whether the subject has discontinued participation in the study, will be followed until resolution, including follow-up of the health status of the newborn to 6 weeks of age.

Pregnancy in itself is not regarded as an AE unless there is a suspicion that investigational product may have interfered with the effectiveness of a contraceptive medication. However, complications of pregnancy and abnormal outcomes of pregnancy are AEs and many may meet criteria for an SAE (such as ectopic pregnancy, spontaneous abortion, intrauterine fetal demise, neonatal death, or congenital anomaly). Elective abortions without complications should not be reported as AEs.

A pregnancy or positive pregnancy test must be reported immediately using the Pregnancy Report Form to the contact information noted. The Investigator must follow-up and document the course and outcome of all pregnancies even if the subject was discontinued from the study. All outcomes of the pregnancy (from a female subject or the partner of a male subject) must be reported on the Pregnancy Report Form by the Investigator after he/she has gained knowledge of the delivery or elective abortion.

Any SAE that occurs during pregnancy must be reported on the SAE form (eg, maternal serious complications, spontaneous or therapeutic abortion, ectopic pregnancy, stillbirth, neonatal death, congenital anomaly, or birth defect) in accordance with SAE reporting procedures.

The effects of administration of the study drug regimen on the pregnant female or the developing fetus are unknown. Refer to [Section 5.7.4](#) for detailed information regarding contraception requirements for female and male subjects and pregnancy testing requirements.

